### 4 STUDY DESIGN

#### 4.1 Study Overview

This is a 6-month randomized, single center, double blinded, delayed start study in 50 patients with relapsing remitting multiple sclerosis and identified injury to the anterior visual pathway.

Patients will be randomized 1:1 into two groups: Group A and Group B. Group A will receive 180 days of Bazedoxifene while Group B will receive 90 days of placebo followed by 90 days of Bazedoxifene. Patients will receive two fixed oral tablets of 20mg Bazedoxifene (Conbriza) daily (to be taken at the same time). Patients will be permitted to remain on their standard disease modifying treatment during the course of the study.

Screening data will be reviewed to determine subject eligibility. Subjects who meet all inclusion criteria and none of the exclusion criteria will be entered into the study

## 5 CRITERIA FOR EVALUATION

### 5.1 Primary Efficacy Endpoint

Visual evoked potentials (VEPs) are cortically generated electrical potentials recorded over the scalp in response to a visual stimulus. After stimulation, a transient, cortically generated response is tied to the relevant stimulus (the transient VEP) and consists of a series of potentials that are alternately positive and negative in polarity. They are labeled on the basis of their polarity and latency. In most individuals, the first response of the full- field pattern-reversal VEP recorded mid-occipitally is a negative deflection termed the N75. However, given lack of consistency of both the presence and latency of the N75, by convention full-field VEPs usually are assessed by evaluating the first major positive deflection that occurs in normal individuals at around 100 msec and is therefore designated the P100 component. Latency of the VEP is defined as the time from the stimulus to a pre-specified feature of the record.

Following application of scalp leads by the technician, patients will be seated in front of a CRT screen. VEPs will be performed using a single Nicolet VEP instrument under standardized conditions of luminance, distance and check contrast. Check size will be held at 32 minutes of arc as calculated by the formula  $M = 3438 * W/D$  ( $M$  = minutes of arc;  $W$  = width of an individual check;  $D$  = distance from screen in mm). Standard recording time is approximately 25-30 minutes including the time required for application of the leads. The participant will be instructed to wear corrective lenses if they have them. If they do not, they will be provided with a pair of trial lenses. The primary outcome of interest will be the P100 latency although other parameters may be studied at a later date in secondary analyses.

### 5.2 Secondary Efficacy Endpoints

#### 5.2.1 Expanded Disability Status Scale (EDSS)

EDSS Score will be determined, based on neurological examination, by a trained certified EDSS rater at scheduled visits according to Appendix-1 using the validated Neurostatus scoring system. Whenever possible, individual patients will have EDSS performed by same rater on each visit.

The EDSS is an ordinal scale used for assessing neurological impairment of MS based on a neurological examination. It consists of scores in each of seven functional systems (FS) and an ambulation score that are then combined to determine the EDSS [ranging from 0 (normal) to 10 (death due to MS)]. The FSs are the Visual, Brain Stem, Pyramidal, Cerebellar, Sensory, Bowel & Bladder, and Cerebral functions. The FSs and EDSS steps will be assessed in a standardized

manner. EDSS is a widely used and accepted instrument to evaluate disability status at a given time and longitudinally, to assess disability progression in clinical studies in MS.

Disability progression based on the EDSS is defined as an increase from baseline of 1 point (in patients with a baseline EDSS score of 3.0 to 5.0 inclusive) or of 0.5 point (in patients with a baseline EDSS score of 5.5 to 6.5 inclusive). To confirm that the progression is sustained, this increase should, at a minimum, be present at a visit at least 3 months later (for 3-month confirmed disability progression) with any intervening EDSS values also meeting the criteria for change.

Analysis of disability progression based on the EDSS score will include variables such as:

- Time to 3-month confirmed disability progression
- Proportion of patients free of a 3-month confirmed disability progression

### 5.2.2 Magnetic Resonance Imaging (MRI)

All patients will undergo MRI scanning of the brain according to the schedule in Appendix-1. MRI evaluation will include, but is not limited to:

Sequences:

- Magnetization Transfer Ratio (5 minutes)
- Radial diffusivity on Diffusion Tensor Imaging (9 minutes)
- T1, FLAIR (10 minutes)
- 3D T2 star (10 minutes)
- Number of new/ enlarging T2 hyperintense lesions
- Total volume of T2 lesions
- Volume of T1 hypointense lesions
- Change in brain volume

All images will be obtained on a Siemens Skyra 3T MRI in the Sandler Neurosciences Building. All scans will be performed by a trained MRI technician using protocols previously defined within the lab (specific MR settings to be defined elsewhere).

Each MRI scan performed for the study, both scheduled and unscheduled (e.g. ordered by the investigator for safety or differential diagnosis), will be reviewed by a neuroradiologist and the primary treating physician must be contacted in case of unexpected findings (not consistent with optic neuritis) detected on the MRI scan for safety actions and Adverse Event reporting.

During the study each scan performed, both scheduled and unscheduled, will be assessed by the blinded trained physician from the NICMSMRI team. Upon acquisition the MRI will be evaluated for quality, completeness, and adherence to the manual. Confirmation of MRI quality or a description of the quality problems, if detected, will be communicated to the investigators. If scan is incomplete or incorrectly performed, the study center will be asked to repeat it as soon as possible. After completion of the quality check, all scans will be analyzed according to a standardized procedure.

Scanning:

All sequences will be performed according to lab specifications.

MRI scans will include MTR, Diffusion tensor imaging, myelin water fraction, T1-weighted images, T2-weighted, Proton Density-weighted and FLAIR images.

### 5.2.3 Cognition

#### 5.2.3.1 Symbol Digit Modalities Test (SDMT)

The SDMT will be assessed according to the schedule in Appendix-1 (study coordinator to administer). The SDMT is a sensitive and specific test to assess processing speed and working memory which are typically affected domains in cognitively impaired MS patients. During the administration of the SDMT, only the examiner and the patient should be in the testing room. The examiner can be the study coordinator, independent EDSS rater or a qualified individual not involved in the treatment of the patients who has been instructed in the appropriate administration of the test. Patients are presented with a test instrument at the top of which there is a row of nine numbers paired with unique symbols. Below this part of the test instrument is an array of symbols paired with empty spaces, the patient's task is to match the number for each symbol as quickly as possible. The test takes approximately 5 minutes to administer. The test scoring is calculated based on the number of correct answers in 90 seconds.

#### 5.2.3.2 Additional cognitive tests

Each study participant will complete approximately 10-15 minutes of cognitive testing as part of three separate study visits (baseline visit, 3-month visit, 6-month visit). The cognitive measures will be administered by a trained study research assistant at the UCSF Multiple Sclerosis Center. In addition to the SDMT, participants will complete the California Verbal Learning Test-II (CVLT-II), an assessment of verbal learning and memory with robust normative data in both healthy and MS populations. This task involves the immediate recall of a list of 16 nouns read aloud by the evaluator at one-second intervals.

### 5.2.4 High Contrast / Low Contrast Visual Acuity (LCVA)

Visual acuity will be assessed according to the schedule in Appendix-1. Disturbances in visual function are common in patients with optic neuritis but these impairments are often not readily apparent on commonly used high-contrast acuity tests. The use of low-contrast visual acuity charts has therefore gained validity in the assessment of visual acuity in patients with optic neuritis. Low contrast Sloan letter charts provide a practical, quantitative, and standardized assessment of visual function. Each chart consists of rows of gray letters, decreasing in size from the top to the bottom row, on a white background. A complete set consists of 7 charts, each with a different level of contrast ranging from 100% (normal vision chart) to 0.6%. For this study only two charts will be used, the 100% (normal vision chart) and 2.5% contrast charts.

When these charts are being rated it is important that standardized conditions are used (e.g. distance from the chart, lighting conditions). For high contrast testing, participants will be seated 4 meters from the chart. For low contrast testing, participants will be seated 2 meters from the chart. Letter scores indicate the number of letters identified correctly, each chart is scored separately. In both cases, testing will be conducted in a low-luminance setting.

Low-contrast letter acuity testing with Sloan charts is easy to administer and has been shown to have high inter-rater reliability both in patients with optic neuritis and in healthy volunteers. The participant will be instructed to wear corrective lenses if they have them. If they do not, they will be provided with a pair of trial lenses.

To ensure consistency amongst raters and between sites, a standard prompt will be utilized for test administration. The administrator will ask the participant to begin at the top line of the chart, reading each line completely and down as many lines as possible. When the

participant finishes reading the chart, they will be prompted by the tester one time: "Please give the next line your best attempt." The tester may continue to encourage the participant following the successful (greater than or equal to 4/5 letters correct) completion of each line until the participant can read no further.

### 5.2.5 Optical Coherence Tomography (OCT)

OCT will be assessed according to the schedule in Appendix-1. Optical Coherence Tomography (OCT) is a noninvasive, noncontact, trans-pupillary imaging technology which can depict retinal structures *in vivo* with high resolution cross-section images of the retina (axial resolution of 3- 5 microns). Cross-sectional images of the retina are produced using the optical backscattering of light in a fashion analogous to B-scan ultrasonography. Whereas ultrasound produces images from backscattered sound "echoes," OCT uses infrared light waves that reflect off the internal microstructure within the biological tissues. The frequencies and bandwidths of infrared light are orders of magnitude higher than medical ultrasound signals -- resulting in greatly increased image resolution approximately 8-25 times greater than any existing modality. In addition, the anatomic layers within the retina can be differentiated and retinal thickness can be measured.

Infrared light is delivered to the imaging site through a single optical fiber only .006" diameter (about the size of the period in this sentence). The imaging guide wire contains a complete lens assembly to perform a variety of imaging functions. Guide wire can be deployed independently or integrated into existing therapeutic or imaging catheters.

While standard electronic techniques are adequate for processing ultrasonic echoes that travel at the speed of sound, interferometric techniques are required to extract the reflected optical signals from the infrared light used in OCT. The output, measured by an interferometer, is computer processed to produce high-resolution, real time, cross sectional or 3-dimensional images of the tissue. This powerful technology provides *in situ* images of tissues at near histological resolution without need for excision or processing of the specimen.

Image scanning will be performed on a Heidelberg Spectralis Spectral Domain OCT instrument. Scanning protocols will include peripapillary B scan and 19 B scan Macular raster scan with target ART of 100 and 50 respectively. Quality targets will be 25 for all studies and only studies with Q> 20 will be analyzed.

### 5.2.6 Health Status Questionnaire (SF-36)

For this study, a Health Status Questionnaire will be administered to patients at the three time-points indicated in Appendix-1. The questionnaire falls under the comprehensive Multiple Sclerosis Quality of Life Inventory (MSQLI), which was developed by The Consortium for Multiple Sclerosis Centers Health Sciences Research Subcommittee as a comprehensive outcomes assessment battery (Fisher et al, 1999), and it will allow us to monitor the participants' quality of life with regard to their health.

The Short Form-36 (SF-36) was derived from the General Health Survey of the Medical Outcomes Study in 1988. As cited by the Multiple Sclerosis Society, it is one of the most widely used generic measures of health-related quality of life and has been shown to discriminate between

subjects with different chronic conditions and between subjects with different severity levels of the same disease. The SF-36 has also demonstrated sensitivity to significant treatment effects in a variety of patient populations.

This tool addresses health issues that are relevant to MS patients from the patient's perspective. The SF-36 generates two summary scores based on 8 subscales. The two scores arrived at are the physical component summary and the mental component summary.

### **5.2.7 Cone Contrast testing**

Rabin cone contrast testing will be performed at the visits indicated in Appendix 1. The test will be performed using an Innova Provideo CCT. Cone sensitivity threshold testing is used to accurately detect shifts that may indicate the onset of eye disease. The participant will be seated so that their eyes are approximately 2 meters from the center of the monitor. They will be instructed to wear corrective lenses if they have them. If they do not, they will be provided with a pair of trial lenses. The participant will be instructed to choose the letter that they see on the screen using a wireless computer mouse. Each eye will be tested individually.

The test presents colors that use only one of your three cones types and shows the color progressively fainter to individually score how the cones are functioning. Using a combination of color and contrast, the Rabin Cone Contrast test is a quantifiable measure of color vision, allowing detection of both hereditary and acquired color vision loss.

Cone contrast testing will be used to assess whether BZA versus placebo has any effect on preservation of color sensitivity.

## **5.3 Safety Evaluations**

### **5.3.1 Physical Examination**

A complete physical examination will be performed by blinded clinician at the visits indicated in Appendix-1 and will include assessment of skin, head and neck, lymph nodes, heart, lungs, abdomen, back, neurological function, and comments on general appearance. All significant findings that are present prior to signing informed consent must be reported on the relevant medical history/ current medical conditions eCRF. Significant findings made after signing the informed consent and being randomized meets the definition of an Adverse Event and must be recorded on the Adverse Event case report form through UCSF's clinical database, REDCap.

### **5.3.2 Vital Signs**

Vital signs will include height, sitting pulse rate, sitting systolic and diastolic blood pressure and body temperature which will be assessed at the visits indicated in Appendix-1.

Clinically notified vital signs are defined in Appendix 1.

### **5.3.3 Height and Weight**

Height will be assessed at the screening visit in centimeters/ inches.

Weight will be assessed in kilograms at the visits indicated in Appendix-1.

Body weight in indoor clothing, but without shoes will be measured. Participants should be asked to remove any items from their pockets and remove any outside clothing such as scarves, jackets, gloves, etc.

#### **5.3.4 Ophthalmologic Examination**

Patients will undergo screening ophthalmologic exam to include assessment for any undiagnosed ophthalmologic disease that could impact assessments including but not limited to dilated examination of the fundus and macula by study investigator. This evaluation will include an eye history, visual acuity measurements and dilated ophthalmoscopy at the screening visit.

Patients with a history of, or active uveitis or a history of macular edema will require special attention.

In addition to visual acuity assessments and dilated ophthalmoscopy, measurement of retinal thickness by OCT and measurement of VEP latency will be conducted at visits as indicated in Appendix-1. The PI will complete an examination of worksheet which will then be transcribed to an ophthalmologic examination eCRF.

#### **5.3.5 Fatigue Assessment**

To ensure patient safety in daily activities, we will conduct a fatigue assessment at each of the visits indicated in Appendix-1, in order to monitor the degree of self-reported fatigue experienced.

The Modified Fatigue Impact Scale (MFIS) is a 21-item fatigue scale that measures the physical, cognitive, and psychosocial aspects of fatigue.

#### **5.3.6 Other Assessments**

MS is associated with a variable combination of symptoms, including sensory loss, imbalance, mobility loss, bladder and bowel dysfunction, cognitive dysfunction, spasticity, pain, and sexual dysfunction. Measurements of these wide-ranging effects of MS on the lives of patients is beyond the scope of the clinician-reported endpoints commonly used to evaluate therapeutic effectiveness in MS studies. Patient-reported outcome (PRO) measures provide an empirical assessment from the patient's perspective of the benefits of treatment that cannot be gained from Magnetic Resonance Imaging (MRI), Expanded Disability Status Score (EDSS), or Optical Coherence Tomography (OCT).

#### **5.3.7 Adverse Event Reporting Plan**

This study is investigator-sponsored and does not involve any outside sponsoring institution to which adverse events should be reported. Serious Adverse Events (SAEs) or unanticipated adverse events, therefore, will be reported internally to the UC San Francisco Committee on Human Research within 10 working days of the event's occurrence according to requirements outlined in the CHR's reporting guidelines.

All adverse events during this study will be recorded in real time in UCSF's HIPAA approved clinical database, REDCap. Recording such events in the same database each patient's trial-based visit records will allow for more efficient tracking and monitoring of all adverse events within the study.

In addition, an inventory of adverse events will be obtained at each visit.

## 6 SUBJECT SELECTION

### 6.1 Study Population

Subjects with a clinically definite diagnosis of MS—according to the 2017 revised McDonald Criteria (Thompson et al., 2017)—who meet the inclusion and exclusion criteria will be eligible for participation in this study.

### 6.2 Inclusion Criteria

1. Women aged 45-65 or 40+ post-menopausal.
2. Documentation of a clinically definite diagnosis of relapsing-remitting MS
3. Written informed consent (and assent when applicable) obtained from subject or subject's legal representative and ability for subject to comply with the requirements of the study.
4. Latency delay > 118 milliseconds on baseline full-field transient pattern reversal VEP in at least one eye (electrophysiological evidence of demyelination)
5. RNFL > 70 microns on SD-OCT in the same eye meeting criteria for latency delay (sufficient axons)
6. Stable immunomodulatory therapy – no switch or planned switch in > 6 months and no change in doses in 30 days prior to screening
7. Use of contraceptive method with  $\leq 1\%$  failure rate during period of trial if premenopausal
8. Understand and sign informed consent.
9. EDSS 0-6.0 (inclusive)

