OF ADMINISTRATION	tablets for the duration of treatment period (180 days for 'Early-start' group and 90 days for 'Delayed-start' group). Tablets will be over-encapsulated in gelatin capsules for proper blinding.
CONTROL PRODUCT, DOSE AND ROUTE OF ADMINISTRATION	Microcrystalline cellulose placebo Product will be taken daily via oral administration of 2 tablets for duration of the treatment period (first 90 days of 'Delayed-start' group ONLY). Tablets will be over-encapsulated in gelatin capsules for proper blinding.
DURATION OF SUBJECT PARTICIPATION AND DURATION OF STUDY	Subjects will be on study for up to 200 days Screening: 2 weeks Treatment: 6 months The total duration of the study is expected to be 24 months, which includes 18 months for subject recruitment.
CONCOMITANT MEDICATIONS	Allowed: MS disease modifying and symptomatic therapies, antidepressants (no adjustments within 2 months of baseline visit) Prohibited: hormone therapies (estrogen, testosterone, progesterone), hot flash therapies; lamotrigine, oxcarbazepine
EFFICACY EVALUATIONS	This study includes the following efficacy assessments: 
 
Detailed neurological examination, including the determination of EDSS score, will take place at the baseline and 6-month visits.
 
Magnetic Resonance Imaging (MRI) scans will be performed at the baseline, 3-month, & 6-month visits.
 
High and Low Contrast Visual Acuity (2.5% ETDRS) will be assessed at every visit.
 
Optical Coherence Tomography (OCT) will be performed at screening, baseline, and 6-month visits.
 
Full-field Visual Evoked Potential will be performed at every visit.
 
Cone contrast testing will be performed at baseline and 6 month visits.
 
 Note: Prior to each visit, participants should be reminded to bring with them any corrective lenses that they use on a regular basis for reading, distance, or both. If the participant does not have or if they forget their corrective lenses, a pair of trial lenses will be provided during the visit.
PRIMARY ENDPOINT	Remyelination assessed by the reduction of P100 VEP latency
SECONDARY ENDPOINTS	[Imaging]: Whole brain MTR, white matter MTR, white matter fractional anisotropy (FA), and MWF. [Functional]: Low-contrast letter acuity (LCLA)
OTHER EVALUATIONS	

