## **10 EVALUATIONS BY VISIT**

### **10.1 Visit 1 (Week 0) - Screening**

1. Review the study with the subject and obtain written informed consent and HIPAA authorization and assent, if appropriate.
2. Assign the subject a unique screening number.

3. Record demographics data.
4. Record medical history, including a history of MS, diagnosis date, and prior MS treatments, as well as history of optic neuritis.
5. Record concomitant medications.
6. Perform a complete physical examination.
7. Perform VEP and OCT assessments (if no record of assessment within past 6 months)
8. Perform and record vital signs.
9. Perform and record results of blood pressure testing.
10. Collect blood for clinical laboratory tests (chemistry, hematology, pregnancy test)
11. Initiate subject diary
12. Schedule subject for Visit 2 in 14 days +/-2.

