### 10.2 Visit 2 (Baseline)

1. Concomitant medications review.
2. Perform abbreviated physical examination.
3. Assess likely side effects via clinician observation and questionnaires
4. Perform and record vital signs.
5. Perform neurologic & ophthalmologic exam.
6. Perform and record visual assessments (OCT, high/low contrast vision testing, cone contrast, VFQ)
7. Perform and record cognitive & other tests (SDMT, MFIS, EDSS, SF-36)
8. Perform timed walking tests (T25W, TUG, 6min walking test)
9. Perform MRI (no contrast)
10. Randomize subject, dispense study drug
11. Collect blood for research laboratory tests (if needed)

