## 15 STATISTICAL METHODS AND CONSIDERATIONS

Prior to the analysis of the final study data, a detailed Statistical Analysis Plan (SAP) will be written describing all analyses that will be performed. The SAP will contain any modifications to the analysis plan described below.

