### 15.3 Analysis of Primary Endpoint

Data will be analyzed per protocol utilizing an intention to treat approach including all patients randomized to the study for the principal analysis. Loss to follow up will be accounted for using standard statistical methods. The principal analysis will be performed using mixed effects linear regression model controlling for clustering by eye.

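### Two pre-treatment VEPs are scheduled, but the primary analysis states no use of both and the sections conflict on which one qualifies the eye; adjusting for both would gain precision at almost no cost

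*Combined protocol and SAP*

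**What the plan says.** - **Number of readings.** The synopsis, under efficacy evaluations, states "Full-field Visual Evoked Potential will be performed at every visit". The VEP row of Appendix 1 marks all four visits. Two readings, Screening and Baseline about 14 days apart, therefore precede treatment.
- **Which reading qualifies the eye.** Inclusion item 4 in 6.2 requires "Latency delay > 118 milliseconds on baseline full-field transient pattern reversal VEP in at least one eye". Section 4.1 states "Screening data will be reviewed to determine subject eligibility".
- **Whether both readings will exist.** The Screening list in 10.1 has "Perform VEP and OCT assessments (if no record of assessment within past 6 months", so an earlier record may replace the Screening test. The Visit 2 list in 10.2 has "Perform and record visual assessments (OCT, high/low contrast vision testing, cone contrast, VFQ", with no VEP.
- **Endpoint and model.** The synopsis gives the primary endpoint as "Remyelination assessed by the reduction of P100 VEP latency", without naming the starting value. Section 15.3 states "The principal analysis will be performed using mixed effects linear regression model controlling for clustering by eye". It mentions no baseline covariate, no change score and no combination of readings.
- **Later plan.** Section 15 promises that "a detailed Statistical Analysis Plan (SAP) will be written describing all analyses that will be performed". That plan is not part of the document reviewed.

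**The concern.** The primary outcome is a reduction in latency, so it needs a defined starting value, and the documents offer two candidates without choosing. Two things are at stake.

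The first is precision. Both readings come before treatment and measure the same quantity in the same eye. A model that adjusts for only one leaves in variance that the other could explain. With 25 patients per arm this matters, and the second reading is already scheduled.

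The second is how within-arm change is read. An eye that enters because a reading exceeded 118 ms is, on average, high on that reading partly by chance. If the same reading also starts the change, latency will appear to fall in both arms without any drug effect. The choice of qualifying reading also affects who enters, because some eyes pass on one reading and not on the other.

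**Working it through.** **The plan's own figure.** Section 15.6 states 90% power with 25 per group at two-sided alpha 0.05. This implies a standardised difference of (1.960 + 1.282) × √(2/25) = 0.917, or 0.936 with the t distribution. The 90% cannot be reproduced in milliseconds, because no SD is given and the base of the 50% reduction is not defined. Half of 118 ms (59 ms) would need an SD of 64 ms. Half of the delay beyond 100 ms (9 ms at the threshold) would need 9.8 ms.

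**Assumptions.** None of these is in the documents: latency before selection has mean 115 ms and SD 12 ms, and any two readings of an eye correlate r = 0.8 to 0.9 in the absence of treatment. The cut of 118 ms then lies (118 − 115)/12 = 0.25 SD above the mean. For a standard normal variable above 0.25, the mean is λ = 0.964 and the variance is v = 0.312.

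**1. Apparent fall if one reading both selects and starts the change.** Expected fall = (1 − r) × SD × λ.
- r = 0.8: 0.2 × 12 × 0.964 = 2.3 ms.
- r = 0.9: 0.1 × 12 × 0.964 = 1.2 ms.
- Measured from the other pre-treatment reading: 0.
- Measured from the mean of the two: half, about 1.2 and 0.6 ms.

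The fall is expected equally in both randomised arms. Under the same assumptions, 25% (r = 0.8) or 17% (r = 0.9) of eyes above 118 ms on one reading are at or below it on the other.

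**2. Residual variance, equal correlations.** In units of the variance before selection:
- Both readings, or their mean: 1 − 2r²/(1 + r) = 0.289 (r = 0.8), 0.147 (r = 0.9).
- The selecting reading alone: 1 − r² = 0.360, 0.190. Using both cuts this by 19.8% and 22.4%.
- The non-selecting reading alone: V − C²/V, where V = r²v + 1 − r² and C = r²v + r − r². At r = 0.8, V = 0.560 and C = 0.360, giving 0.329. At r = 0.9, V = 0.443 and C = 0.343, giving 0.177. Using both cuts this by 12% and 17%. At r = 0.6 to 0.7 the cut is 6% to 9%.

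**3. Unequal correlations, before selection.** The gain from adding Screening (S) to Baseline (B) for the month-3 outcome (Y) is (r_SY − r_SB·r_BY)² / [(1 − r_SB²)(1 − r_BY²)]. Take r_BY = 0.8.
- r_SB = r_SY = 0.7: 0.0196/0.1836 = 10.7%.
- r_SB = r_SY = 0.6: 0.0144/0.2304 = 6.3%.
- r_SB = r_SY = 0.5: 0.0100/0.2700 = 3.7%.
- r_SB = 0.9, r_SY = 0.8: 0.0064/0.0684 = 9.4%.

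These gains assume optimal weights. In the first three cases a plain mean does less well. Its residual variance is 1 − [(0.8 + q)/2]²/[(1 + q)/2], where q = r_SB = r_SY. At q = 0.7 it is 0.338, a gain of 6% on 0.360. At q = 0.6 it is 0.388, which is worse than Baseline alone. An old record should therefore not be averaged in.

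**4. Power, as illustration.** Suppose 90% is the true power of a model adjusting for one reading (standardised difference 0.936, 25 per arm). A cut of 12% to 17% would then give about 93% to 94.5%, and a cut of 20% to 22% about 95% to 96%.

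**The case against.** A reader might infer that the reading which selects the eye is also the start of the change. The documents do not establish this. Section 4.1 points to Screening for eligibility, and nothing defines the starting value. If Screening selects and the Visit 2 reading starts the change, the artefactual fall is zero.

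A reader might also infer that the primary comparison is biased. It is not: allocation is 1:1 at random, and regression to the mean is expected equally in both arms. Only within-arm changes, or a ratio of changes, would be distorted. The one hint of a ratio is the wording of the sample-size statement in 15.6; 15.3 specifies a linear model.

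Nor does any section say that one reading is discarded. Section 15.3 is silent, and the promised SAP could settle the matter.

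The size is open to challenge too. A cut of about a fifth holds only against the selecting reading, with r near 0.8 to 0.9, equal correlations and a model that already adjusts for one reading, which 15.3 does not state. Patients whose Screening value is an earlier record would gain nothing under the fallback, and their number is unknown. The missing VEP in 10.2 may be a drafting slip, since 10.3 and 10.4 omit it as well.

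All of this stands, and it limits the point to precision and clarity. It does not remove the conflict between sections. The SAP cannot settle eligibility after patients have been randomised.

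**Conclusion.** The point holds as a missed, nearly free gain in precision on the primary endpoint, together with a real conflict over the qualifying reading. Relative to adjusting for one reading, the expected cut in residual variance is about 12% to 17% if that reading did not select the eye, and at most 20% to 22% if it did, for r of 0.8 to 0.9 and equal correlations. It is about 4% to 11% if the Screening reading is older or less correlated, and smaller still for the trial as a whole if many patients have only one study reading. A spurious within-arm fall of about 1 to 2 ms arises only if one reading both selects the eye and starts the change. The difference between Group A and Group B at 90 days is not biased. All magnitudes rest on an assumed mean, SD and correlation, so confidence is moderate. The change should be made before analysis, and the eligibility wording settled before enrolment.

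**What to change.** 1. In 15.3 and the SAP, specify P100 latency at 3 months as the outcome for each eye, with that eye's pre-treatment latency as a covariate. Use the mean of the Screening and Baseline VEPs where both are study recordings, and the Baseline VEP alone where Screening is an earlier record. State the SD and correlation assumed.
2. Report within-arm change from the reading that did not select the eye. Do not report it from the mean, which keeps half of the artefact.
3. Reconcile the synopsis, 4.1, 6.2 item 4, 10.1, 10.2 and Appendix 1 so that one named VEP decides eligibility and a VEP is listed at Visit 2. Appendix 1 also marks randomisation at Screening while 10.2 places it at Visit 2; align these at the same time.

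The cost is a few lines of text and no extra test. The drawback is a covariate measured less precisely in patients with only one study reading.
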